### **4.7.2 Lost to Follow-Up**

All reasonable efforts must be made to locate participants to determine and report their ongoing status. This includes follow-up with those authorized by the participant as noted above. Lost to follow-up is defined as the inability to reach the participant after a minimum of three documented phone calls, faxes, or emails as well as lack of response by participant to one registered mail letter. All attempts should be documented in the participant's medical records. If it is determined that the participant has died, the site will use permissible local methods to obtain the date and cause of death.

If investigator's use of third-party representative to assist in the follow-up portion of the study has been included in the participant's informed consent, then the investigator may use a third-party representative to assist site staff with obtaining participant's contact information or other public vital status data necessary to complete the follow-up portion of the study. The site staff and representative will consult publicly available sources, such as public health registries and databases, to obtain updated contact information. If after all attempts the participant remains lost to follow-up, then the last known alive date as determined by the investigator should be reported and documented in the participant's medical records.

## 5 RADIATION THERAPY

### 5.1 Thoracic Radiation Dose Specifications

Patients will receive thoracic radiation to residual intrathoracic disease including mediastinal, supraclavicular (SC), and hilar lymph node sites involved at the time of diagnosis. The treating physician will have discretion to limit treatment volume if there is concern for excess of normal tissue irradiation.

The total dose of 30 Gy will be given in 10 daily fractions of 3 Gy prescribed to the planning target volume (PTV) with at least 95% of the PTV receiving 30 Gy. An acceptable variation is at least 90% of the PTV receiving 30 Gy. The maximum dose for any contiguous volume of no more than 0.03 cc inside the PTV must not exceed 120% of the prescribed dose. An acceptable deviation is a maximum dose inside the PTV of up to 125% of the prescribed dose. The minimum dose (0.03 cc) to the PTV volume should be no less than 28.5 Gy. An acceptable deviation is a minimum PTV dose of 27.9 Gy. All radiation doses will be calculated with inhomogeneity corrections.

### 5.2 Radiation Treatment Schedule

Localization, Simulation, and Immobilization for radiation treatment planning, as outlined in Section 5.4, will be performed no more 21 days and no less than 1 day before the first day of thoracic radiation treatment. The patient can initiate treatment any day of the week. Treatment will be delivered daily for 10 consecutive working days (generally Monday-Friday). Disruptions to the planned radiation treatment schedule should be avoided if at all possible. Any unexpected treatment break lasting > 1 day should be reported to the principal investigator.

**Table 5.2-1.** Radiation Treatment Schedule

Thoracic RT Planning Simulation	Radiation Treatment 1-5	Radiation Treatment 6-10
Between Day -21 and Day 0	Week 1	Week 2 

If thoracic radiation therapy is started later in week 1, then radiation treatments will continue into week 3.

## 5.3 Technical Factors

### 5.3.1 Beam Energy

Six- to 10-MV photons are recommended for mediastinal and lung irradiation; however, beam energy and type will be left to the discretion of the treating radiation oncologist in order to obtain the best dose distribution for the site being treated.

### 5.3.2 Beam Shaping

Multi-leaf collimation (MLC) or individually shaped custom blocks should be used to protect normal tissues outside of the target volume.

## 5.4 Localization, Simulation, and Immobilization

A volumetric treatment planning computed tomography (CT) study (intravenous contrast preferred, if possible) will be required for treatment of primary disease and regional lymphatics. A four-dimensional CT to account for respiratory motion may be beneficial and should be utilized whenever possible to limit the overall size of the planning target volume. PET-CT performed for restaging may also assist with radiation treatment planning target delineation. Evaluation and/or fusion (according to each institution's standard practice) of the initial diagnostic PET-CT or CT chest will assist with delineation of any initially involved hilar or mediastinal nodal sites.

Each patient will be positioned in an immobilization device in the treatment position on a flat table. Contiguous CT slices with a no more than 3-mm thickness will be obtained through the regions harboring gross disease and the entirety of all organs in the treatment field. This is necessary for proper radiation planning.

## 5.5 Treatment Planning/Target Volumes

The definitions of volumes will be in accordance with the 1993 ICRU Reports #62.

*Definition of GTV:* Gross tumor volume (GTV) will include known disease as determined by physical examination and post-chemotherapy imaging studies. The Uniform Tissue Naming scheme for this study is available in Table 5.6-2.

*Definition of CTV:* The clinical target volume (CTV) will be defined as any residual intrathoracic disease contoured as GTV plus 0-1cm (preferable 0.7cm) expansion volume accounting for anatomic boundaries. Additionally, the CTV volume will include any SC, hilar or mediastinal lymph node sites that were involved at the time of initial diagnosis. This is not the same as pretreatment volume. For example, if the patient had a 10 cm mediastinal mass that involved the paratracheal and subcarinal lymph nodes and had a complete response to chemotherapy, the CTV would not necessarily be a 10 cm volume but rather a carefully defined volume including the subcarinal and paratracheal tissues. CTVs will be labeled to correspond to the appropriate GTV or in cases where there is no GTV, the CTV will be labeled according to Uniform Tissue Naming scheme in Table

5.6-2.CTV may be modified to exclude intrathoracic pulmonary nodules as well as nodal regions if they contribute to excess normal tissue toxicity.

*Definition of PTV:* The planning target volume (PTV) is the CTV plus a margin to account for treatment set-up uncertainty and organ motion. The most appropriate PTV margin is to be determined by the treating radiation oncologist and could range from 0.3 to 2.0 cm depending on the use of respiratory motion management and image guided radiation therapy techniques.

Utilization of advanced planning techniques including 3D conformal radiation therapy (3DCRT) or intensity modulated radiation therapy (IMRT) to minimize dose to normal tissues (especially lung) is encouraged.

*Respiratory Motion Assessment and Management:*

Utilization of advanced planning techniques to account for respiratory motion can limit the volume of normal tissue (specifically lung). By utilizing respiratory motion management, the PTV margin that accounts for organ motion can be made smaller. 4D-CT based planning to account for any residual tumor motion as well as hilar-mediastinal motion is one form of respiratory motion management. Alternative options to account for respiratory motion include but are not limited to fiducial marker placement, gating and breath hold approaches.

*Internal Target Volume (ITV) Approach:*

If a 4D-CT was collected at the time of simulation for respiratory motion management, then an ITV approach can be utilized to account for internal motion. Utilization of an ITV approach allows for limiting PTV expansion as outlined above. ITV approach can be utilized to account for motion of any residual intrathoracic tumor through designation of GITV or it can be utilized to delineate CTV motion at the hilar or mediastinal sites through designation of a CITV.

*3DCRT Treatment Planning:*

The PTVs are to be treated with any combination of coplanar or non-coplanar 3-dimensional conformal fields shaped to deliver the specified dose while restricting the dose to normal tissues. Field arrangements will be determined by the 3D planning to produce the optimal conformal plan in accordance with volume definitions. The treatment plan used for each patient will be based on an analysis of volumetric dose, including DVH analysis of the cumulative dose to each PTV and all critical normal structures.

*IMRT Treatment Planning:*

IMRT is allowed at the discretion of the treating radiation oncologist. If IMRT is used, it is highly encouraged that a 4D-CT is also performed.

## 5.6 Target Volume and Critical Structure Constraints with Compliance Criteria

Table 5.6-1. Target Volume and Critical Structure Constraints with Compliance Criteria			
Structure	Dose Constraint	Acceptable Variation	Unacceptable Deviation
PTV	30Gy $\geq 95\%$	30Gy $\geq 90\%$	30Gy $< 90\%$
	Min (0.03cc) $> = 28.5\text{Gy}$	Min (0.03cc) $> = 27.9\text{Gy}$	Min (0.03cc) $< 27.9\text{Gy}$
	Max (0.03cc) $\leq 36\text{Gy}$	Max (0.03) $\leq 37.5\text{Gy}$	Max (0.03) $> 37.5\text{Gy}$
Lungs	V20Gy $\leq 20\%$	V20Gy $\leq 35\%$	V20Gy $> 35\%$
	Mean $\leq 15\text{Gy}$	Mean $\leq 20\text{Gy}$	MLD $> 20\text{Gy}$
Liver	$> 700 \text{ cc} \leq 10 \text{ Gy}$	$> 700 \text{ cc} \leq 18 \text{ Gy}$	$< 700 \text{ cc} \leq 18 \text{ Gy}$
Spinal cord	Max (0.03cc) $< = 36\text{Gy}$	NA	Max (0.03cc) $> 36\text{Gy}$
Heart	Max (0.03cc) $< = 36\text{Gy}$	Max (0.03cc) $> 36\text{Gy}$	NA
	V30Gy $\leq 30\%$	V30Gy $> 30\%$	Min (0.03) $> 30\text{Gy}$
Esophagus	Max (0.03cc) $\leq 36\text{Gy}$	Max (0.03cc) $> 36\text{Gy}$	NA

Note: All required structures must be labeled as listed in the table below for digital RT data submission. Resubmission of data may be required if labeling of structures does not conform to the DICOM standard name listed.

Table 5.6-2 outlines the naming of the various normal and critical structures for radiation treatment plan submission.

Table 5.6-2. Uniform Tissue Naming Scheme and Descriptions	
DICOM Standard Name	Description
GTV	Gross Tumor Volume Required for lesions that have not had CR to chemotherapy unless using GITV
GITV	Gross Internal Tumor Volume (*if using ITV approach) Optional
CTV	Clinical Target Volume Required - unless using CITV
CITV	Clinical Internal Target Volume (*if using ITV approach) Optional
PTV	Planning Target Volume Required
Lungs	Right Lung + Left Lung minus GTV Required
Heart	Heart/Pericardium Required
Esophagus	Esophagus Required
Spinal Cord	Spinal Cord Required
Non-PTV	External minus PTV Required
Liver	Liver (*if in path of beam) Optional

## 5.7 Documentation Requirements

Portal images of each field must be obtained on or before the first day of therapy but will not be submitted.

If IMRT is used, portal images will not be obtained, but patient specific QA will be performed prior to the first fraction.

Verification films of each site will be done weekly, but not submitted.

Cone beam CT, kV imaging, or other in-room imaging for set-up is allowed.

Isodose plans for 3D radiotherapy or IMRT planning with DVHs of GTV, CTV, PTV, and critical structures are required.

Acceptable variations are allowed only when the geometrical arrangement of the target and critical structures is challenging. Unacceptable deviations should be avoided whenever possible and plan modifications should be attempted to improve results. Ultimately, the decision to deliver the proposed radiation treatment plan falls to the treating radiation oncologist. The details of each radiation treatment plan are to be collected by the study sponsor and all acceptable variations and unacceptable deviations will be appropriately documented in the study record.

## **5.8 Radiation Therapy Quality Assurance Reviews**

The Radiation Oncology Principal Investigator, [name], or designee, will perform an RT Quality Assurance review for the first case from each study site prior to initiation of radiation therapy. At least 3 business days should be allowed for case review. Once the initial case from each institution has been carefully reviewed and deemed acceptable, all other patients will be treated according to the protocol guidelines by the treating radiation oncologist. All cases will be reviewed within 3 months after the study has reached the target accrual or as soon as complete data for all cases enrolled have been received at Moffitt Cancer Center.

## **5.9 Radiation Therapy Adverse Events**

Side effects of treatment will vary depending on the location of disease and volume of normal tissues in or near the radiation planning target volume. All attempts should be made to minimize adverse effects by limiting the normal tissue radiation dose (especially to the lung) as much as possible and adhering to the normal tissue dose constraints of this study.

### **5.9.1 Acute Reactions**

It is likely that all patients treated on study will develop some level of fatigue. Alopecia, skin hyperpigmentation, and erythema are possible acute side effects that are generally well tolerated. Cough and esophagitis (if the esophagus is within or near the planning target volume) are likely. Severe esophagitis requiring intravenous hydration, therapy interruption, or feeding tube, severe cough, shortness of breath, and hemoptysis are possible but less likely.

### **5.9.2 Late Reactions**

Asymptomatic fibrotic changes in the lung seen on chest imaging are likely. Severe fibrosis of lung resulting in severe respiratory compromise, symptomatic esophageal stricture, radiation pericarditis, and myocardial injury, spinal cord injury, and brachialplexopathy are possible but unlikely adverse effects of radiation.

### 5.9.3 Treatment of Radiation Adverse Events

All attempts should be made to limit the symptoms and the overall impact of acute and late effects of radiation. Esophagitis should be treated empirically for candidiasis with fluconazole or nystatin, and managed with topical anesthetic, H2 blocker or proton pump inhibitor, NSAIDs, or narcotic pain medications, if necessary.

## 6 STUDY DRUGS

Study drugs include both Investigational [Medicinal] Product (IP/IMP) and Non-investigational [Medicinal] Product (Non-IP/Non-IMP), including the following (**Table 6-1**):

Table 6-1. Study Drugs for MCC 18914				
Product Description/Class and Dosage Form	IP/Non-IMP	Potency	Packaging/Appearance	Storage Conditions (per label)
Nivolumab Solution for Injection	IP	100 mg (10 mg/mL)	10 mL/vial (5 or 10 vials/carton)	Store at 2-8°C; protect from light and freezing
Ipilimumab Solution for Injection	IP	200 mg (5 mg/mL)	40 mL/vial (4 vials/carton)	Store at 2-8°C; protect from light and freezing

Premedications or medications used to treat infusion-related reactions should be sourced by the investigative sites if available and permitted by local regulations. Solutions used as diluent or placebo (ie, 0.9% sodium chloride injection or 5% dextrose injection) should also be sourced by investigative sites if available and permitted by local regulations.

### 6.1 Investigational Product

An investigational product, also known as investigational medicinal product in some regions, is defined a pharmaceutical form of an active substance or placebo being tested or used as a reference in a clinical study, including products already with a marketing authorization but used or assembled (formulated or packaged) differently than the authorized form, or used for an unauthorized indication, or when used to gain further information about the authorized form.

The investigational product should be stored in a secure area according to local regulations. It is the responsibility of the investigator to ensure that investigational product is only dispensed to study participants. The investigational product must be dispensed only from official study sites by authorized personnel according to local regulations. In this protocol, the investigational medicinal products are:

- Nivolumab
- Ipilimumab

## 6.2 Non-investigational Product

Other medications used as support or escape medication for preventative, diagnostic, or therapeutic reasons, as components of the standard of care for a given diagnosis, may be considered as non-investigational products. Non-investigational products should be sourced by the investigator sites if available and permitted by local regulations.

## 6.3 Storage of Study Drug

The product storage manager should ensure that the study drug is stored in accordance with the environmental conditions (temperature, light, and humidity) as outlined in the investigator's brochure. If concerns regarding the quality or appearance of the study drug arise, the study drug should not be dispensed and contact the principal investigator and BMS immediately. Study drug not supplied by BMS will be stored in accordance with the package insert. Please refer to Section 10.2.2 for guidance on IP records and documentation. Infusion-related supplies (eg, IV bags, in-line filters, 0.9% sodium chloride injection, 5% dextrose injection) will not be supplied by the sponsor and should be purchased locally if permitted by local regulations. Please refer to the current version of the Investigator Brochure (IB) and/or pharmacy reference sheets for complete storage, handling, dispensing, and infusion information for nivolumab and ipilimumab. The infusion duration of nivolumab is 30 minutes and for ipilimumab is 90 minutes.

## 6.4 Method of Assigning Participant Identification

Every participant that signs the informed consent form must be assigned a participant number. The investigator or designee will register the participant for enrollment by following the enrollment procedures established by principle investigator.

All participants must be registered with the MCRN Coordinating Center to be able to participate in a trial. The participating site must fax or email the completed study specific eligibility checklist and registration forms, supporting documents and signed informed consent to the Coordinating Center. Unsigned or incomplete forms will be returned to the site. Once documents are received, the MCRN Research Coordinator will review them to confirm eligibility and to complete the registration process. If eligibility cannot be confirmed, the research coordinator will query the site for clarification or additional documents as needed. Participants failing to meet all study eligibility requirements will not be registered and will be unable to participate in the trial.

Upon completion of registration, the MCRN Research Coordinator will provide the participating site with the study sequence number, if indicated. Within 24-48 hours after registration, it is the site's responsibility to:

- Enter the demographic and on-study patient information into the Oncore database
- Order investigational agent(s) if indicated per protocol

It is the responsibility of the participating Investigator or designee to inform the participant of the research treatment plan and to conduct the study in compliance with the protocol as agreed upon with Moffitt Cancer Center and approved by the site's IRB.

To register a patient, the completed and signed eligibility checklist along with supporting documentation must be sent to the MCRN via email at [[contact]](mailto:[contact]) or via fax at [contact], Monday through Friday between 8:00AM and 5:00PM (EST).

## 6.5 Selection and Timing of Dose for Each Participant

The dosing schedules are detailed in Table 6.5-1.

Table 6.5-1. Dosing Schedule (Cycles 1-3)		
Cycles 1 and 2 (42-day [6 week] cycles)		Cycle 3 (28-day [4 week] cycles)
Day 1	Day 22	Day 1
1 mg/kg Nivolumab (diluted to 100 mL)	1 mg/kg Nivolumab (diluted to 100 mL)	480 mg Nivolumab (48 mL diluted 100 mL)
3 mg/kg Ipilimumab (diluted to 100 mL)	3 mg/kg Ipilimumab (diluted to 100 mL)	

For participants weighing < 35 kg, nivolumab and ipilimumab must be diluted to 50 mL in 0.9% sodium chloride or 5% dextrose solution.

All participants will be monitored continuously for adverse events (AEs) while on study treatment. Treatment modifications (eg, dose delay or discontinuation) will be based on specific laboratory and AE criteria, as described in Sections 6.5.3.

When study drugs (ipilimumab or nivolumab) are to be administered on the same day, separate infusion bags and filters must be used for each infusion. Nivolumab is to be administered first. The second infusion will always be the ipilimumab study drug and will start no sooner than 30 minutes after completion of the nivolumab infusion.

Ipilimumab must be diluted to 100 mL in 0.9% sodium chloride solution or 5% dextrose solution. Nivolumab must be diluted to 100 mL 0.9% sodium chloride solution or 5% dextrose solution. For weight-based dosing, if the participants weight on the day of dosing differs by > 10% from the weight used to calculate the dose, the dose must be recalculated. All doses should be rounded up or to the nearest milligram per institutional standard. There will be no dose modifications allowed.

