### 4.2 Phase I/II Study Design and Duration

This is a non-randomized, single-arm, multicenter, phase I/II study in adult patients with ED-SCLC, who achieved stable disease, partial response, or complete response after completion of platinum-based first-line chemotherapy. Fifty participants will be enrolled to receive thoracic radiation therapy (30 Gy in 10 fractions) followed by nivolumab/ipilimumab combination therapy for 4 cycles and then maintenance nivolumab until progression. The study design schematic is presented in Figure 4.2-1.

**Figure 4.2-1.** Study Schematic

The treatment regimen is as follows:

At least 3 weeks, but not longer than 8 weeks after completion of systemic chemotherapy, patients will initiate thoracic radiation therapy targeting the initially involved supraclavicular, hilar and mediastinal lymph node stations as well any other residual intrathoracic disease seen on restaging CT or PET-CT after completion of systemic therapy. Details of the Radiotherapy Treatment Schedule are outlined in Table 5.2-1. At least 14 days and not more than 21 days after completion of RT, patients will commence nivolumab 1 mg/kg (30-minute IV infusion) and ipilimumab 3 mg/kg (90-minute IV infusion) every 3 weeks for 4 doses, followed by nivolumab 480 mg every 4 weeks, as described in Table 6.5-1.

The detailed 3-part schedule of investigational treatments is as follows:

- 1)** Monday to Friday: thoracic radiation therapy at a dose of 3 Gy daily for 10 treatments
- 2)** After at least 14 days but not more than 21 days, initiate combined nivolumab 1 mg/kg + ipilimumab 3 mg/kg every 3 weeks for 4 doses;
- 3)** After part 2 of treatment, initiate maintenance nivolumab at least 42 days but not more than 56 days, delivered every 4 weeks at a dose of 480 mg/cycle.

Patients will undergo ongoing 4-week cycles until discontinuation criteria are met (Section 4.6). The full study schedule calendar is outlined in Appendix 1.

On-study tumor assessments commence 4 weeks after initiation of thoracic radiation therapy and will be conducted according to the study calendar schedule(+/-5 days) for the first 33 weeks. After week 36, radiographic tumor assessments will be performed every 12 weeks (+/-5 days) until disease progression (See Tables 7.4-1 and 7.4-2).

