### **6.5.1 Dosing Windows**

During Cycles 1 and 2:

- Participants may be dosed with ipilimumab 3 mg/kg and nivolumab 1 mg/kg with no less than 19 days between
  - C1D1 and C1D21
  - C1D21 and C2D1
  - C2D1 and C2D21
  - C2D21 and C3D1

During Cycle 3 and beyond:

- Participants may be dosed no less than 27 days from the previous dose of drug

Participants may be dosed up to 3 business days after the scheduled date if necessary, or longer in the event of a toxicity requiring dose delay. Subsequent dosing should be based on the actual date of administration of the previous dose of drug. Treatment compliance will be monitored by drug accountability as well as the participant's medical record and eCRF.

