### **6.5.2 Study Medications**

Nivolumab 1 mg/kg (30 min IV infusion) and ipilimumab 3 mg/kg (90 minute IV infusion) will be administered every 3 weeks for 4 doses, followed by nivolumab 480 mg every 4 weeks. The rationale for this dose schedule is provided in Section 1.1.7. The schedule of investigational treatments is divided into two 42-day cycles at the start of therapy, followed by ongoing 4-week cycles. This dosing schedule is described in detail in Table 6.5-1.

Refer to the Pharmacy Information sheets for more detail. There are no pre-medications recommended on the first cycle. If an acute infusion reaction is noted, participants should be managed according to Section 6.5.6. See Section 6.5.4 for information on Management Algorithms for Immuno-Oncology Agents.

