### **6.5.3 Dose Modifications and Delays**

#### **6.5.3.1 Dose Modifications**

Dose reductions and discontinuation of ipilimumab or nivolumab for the management of toxicities of individual participants are permitted at the discretion of the treating physician. Dose escalations are not permitted.

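### Section 6.5 bars dose modifications that 6.5.3.1 permits, and Table 6.5-1 implies the first maintenance dose at 21 days where 4.2 and Table 7.1-4 require 42 to 56

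*Combined protocol and SAP*

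**What the plan says.** **Dose reductions.** Section 6.5 says "Treatment modifications (eg, dose delay or discontinuation) will be based on specific laboratory and AE criteria" and refers to section 6.5.3 for those criteria. It closes its paragraph on dilution, weight recalculation and rounding with "There will be no dose modifications allowed". Section 6.5.3.1 says "Dose reductions and discontinuation of ipilimumab or nivolumab for the management of toxicities of individual participants are permitted", at the treating physician's discretion, and rules out only escalation. Grade criteria follow for delay (6.5.3.2) and for discontinuation (6.5.3.4). There are none for reduction, and no reduced dose level is given.

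**Start of maintenance.** Table 6.5-1 shows Cycles 1 and 2 as 42-day cycles with combination doses on Days 1 and 22, and Cycle 3 as a 28-day cycle with 480 mg nivolumab on Day 1. Section 6.5.2 puts it as "The schedule of investigational treatments is divided into two 42-day cycles at the start of therapy, followed by ongoing 4-week cycles". Section 6.5.1 lists the pair "C2D21 and C3D1" under its 19-day minimum, and for Cycle 3 onward says "Participants may be dosed no less than 27 days from the previous dose of drug".

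Part 3 of the schedule in section 4.2 says to "initiate maintenance nivolumab at least 42 days but not more than 56 days, delivered every 4 weeks", counted from the end of part 2. Footnote A to Table 7.1-4 gives the same 42 to 56 days, counted from when Cycles 1 and 2 are complete. Section 4.2 also describes the regimen as combination treatment "followed by nivolumab 480 mg every 4 weeks, as described in Table 6.5-1", and sections 4.2.1 and 6.5.2 point to the same table.

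**The concern.** These are current operative dosing instructions, and they give different answers to two practical questions: may a dose be reduced, and when is the first 480 mg dose due?

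A pharmacy working from Table 6.5-1 would give that dose three weeks before the earliest date in section 4.2. A site working from section 4.2 or Table 7.1-4 would wait. Section 9.2.1 names one lead institution and up to five others, so exposure and the handling of toxicity could vary by site without anyone breaking the passage they followed.

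Reductions matter most in Part 1, whose stated purpose is to confirm the recommended dose in 6 to 9 patients. If some lead-in patients are reduced at discretion, to levels nobody has specified, it becomes unclear which dose was confirmed.

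**Working it through.** **Reductions.** This part is textual. Section 6.5 forbids modification and names delay and discontinuation as its examples of what may be done. Section 6.5.3.1 adds reduction. Even if 6.5.3.1 prevails, the rule is incomplete, because 6.5.3 gives no trigger and no level for a reduction.

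**Timing.** Count the first combination dose as day 1.

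- Combination doses every 21 days (Table 6.5-1, section 6.5.2): days 1, 22, 43 and 64. The fourth dose is on day 64.
- First day after two contiguous 42-day cycles: 2 × 42 + 1 = day 85. Gap from the fourth dose: 85 − 64 = 21 days.
- End of Cycle 2: 2 × 42 = day 84.

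| Source and reading | First 480 mg dose | Days after fourth dose |
|---|---|---|
| Table 6.5-1 and 6.5.2, contiguous cycles | day 85 | 21 |
| 6.5.1, 19-day minimum | day 64 + 19 = 83 or later | at least 19 |
| 6.5.1, 27-day minimum, if it covers the first Cycle 3 dose | day 64 + 27 = 91 or later | at least 27 |
| 4.2 and Table 7.1-4, counted from the fourth dose | days 64 + 42 = 106 to 64 + 56 = 120 | 42 to 56 |
| Table 7.1-4 footnote, counted from the end of Cycle 2 | days 84 + 42 = 126 to 84 + 56 = 140 | 62 to 76 |

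The table's date precedes the earliest section 4.2 date by 106 − 85 = 21 days. Only counting from Cycle 2 Day 1 (day 43) would reconcile the two, giving days 85 to 99. That does not fit wording that starts the count once part 2, or Cycles 1 and 2, is finished.

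**Which date was meant.** In the Appendix 1 calendar the combination footnote sits on W4 and the nivolumab-alone footnote on W19. With day 1 as the first day of W4, week = 4 + floor((day − 1)/7):

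- day 64: 4 + 9 = W13
- day 85: 4 + 12 = W16
- day 106: 4 + 15 = W19
- day 126: 4 + 17 = W21

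W19 matches 42 days after the fourth dose. The columns in the body of the calendar did not survive text extraction, so this rests on the header only. The scan weeks in Table 7.4-1 (19, 27, 35) are 8 weeks apart, or two 4-week cycles from W19, which is consistent with that date.

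**Knock-on rules.**

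- Section 6.5.1 allows dosing up to 3 business days after the scheduled date, or later for toxicity. If day 85 is the scheduled date, day 106 is out of window.
- Sections 4.5.2 and 6.5.3.4 set a limit of 6 weeks (42 days) from the last dose. If the 42 to 56 days run from the fourth dose, a gap of 43 to 56 days is permitted by section 4.2 and exceeds that limit.
- Section 4.1 anchors the 13-week safety period both to radiotherapy start and to combination start. From combination start it covers days 1 to 91 (13 × 7), so a day-85 dose falls inside and a day-106 dose outside. From radiotherapy start, both fall outside.

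**The case against.** The strongest objection is that the 21-day date is stated nowhere. Table 6.5-1 gives dosing days within cycles and no interval to Cycle 3. The only explicit bounded interval is 42 to 56 days, in two places, and it satisfies both minimums in section 6.5.1. The Cycle 2 to Cycle 3 line in 6.5.1 looks like a slip: it sits under a sentence about the combination doses, and it says Day 21 where the table says Day 22. The calendar header and scan weeks then show what was intended. On reductions, section 6.5 defers to 6.5.3, and its closing sentence may concern only dilution and rounding.

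Much of this stands. The date is inferred, the 6.5.1 limits are floors, and 42 to 56 days is the likelier intent. The 62 to 76 day reading is the least plausible, since it misses W19. A careful site could reach the right date by reading everything, and the pharmacy materials, which are not in the documents, may help.

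It does not remove the problem. Three sections send the reader to a table whose natural reading is 21 days, and section 6.5.1 as printed supports that reading. The narrower meaning of the 6.5 sentence is possible but not stated, and no reading supplies a reduction level.

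**Conclusion.** The concern holds: the dosing text is wrong as written. On timing, the first 480 mg dose falls 21 days after the fourth combination dose under Table 6.5-1 and 42 to 56 days after it under section 4.2, a difference of at least 21 days. This assumes contiguous cycles in the table and a count from the fourth dose in section 4.2; counting from the end of Cycle 2 widens the difference. On reductions, one sentence forbids what another permits, and the permission has no level or trigger.

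This should be fixed. It bears on what patients receive and on how the lead-in dose is interpreted. It does not enter the Simon two-stage calculation, so type I error, power and sample size stand, and no effect on PFS is claimed.

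**What to change.** 1. State in section 4.2, Table 6.5-1, section 6.5.2 and footnote A to Table 7.1-4 that Cycle 3 Day 1 falls 42 to 56 days after the fourth combination dose. This agrees with W19 in the calendar.
2. In section 6.5.1, remove the Cycle 2 to Cycle 3 pair from the 19-day list, and limit the 27-day minimum to doses after Cycle 3 Day 1.
3. State that this planned gap is not a treatment break under 4.5.2 or a dosing interruption under 6.5.3.4.
4. Make 6.5 and 6.5.3.1 agree. Either delete the permission to reduce, or limit the 6.5 sentence to what it is meant to cover and state the reduced level.
5. Tabulate any dose reductions among lead-in patients.

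The clinical choice is the sponsor's. If 21 days is what is wanted, section 4.2, Table 7.1-4 and the calendar need changing instead. The cost is amendment wording, with no added procedures or patients.
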